**4.2 Secondary Outcomes:**

- a) total consumption of inpatient opioids in morphine milligram equivalents
- b) surgical outcomes including rapid response, transfer to icu, and ileus
- c) the incidence of side effects, including hallucinations, sedation, adverse reactions requiring early cessation

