### **6.2 Exclusion criteria:**

- allergy or contraindication to ketamine
- unable or refused to receive a neuraxial or regional nerve block
- patient refusal
- direct transfer from operating room to ICU with endotracheal tube placed
- treating team elects to exclude the patient prior to study drug administration
- abortion of surgical procedure

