Adult patients presenting on a weekday for an elective major inpatient abdominal surgery at VUMC will be screened for eligibility. Indications for exclusion will be noted if they meet criteria specified in the study protocol. Two post-randomization exclusions have been prespecified for this study. First, a patient directly transferred from the operating room to the Intensive Care Unit (ICU) with an endotracheal tube placed will not be included. The rationale is that these patients are exposed to both a sedative and narcotic infusion for the duration of their intubation, which would confound the ability to determine analgesic efficacy and/or side effects from the study drug. Furthermore, Enhanced Recovery After Surgery (ERAS) protocols are not followed in the ICU, and therefore there would be significant deviations from study protocol. Importantly, we aim to study ketamine's effects within ERAS principles for specifically elective surgeries. A transfer to the ICU while intubated reflects the occurrence of a major, unintended, and unanticipated intraoperative event for these elective procedures. The focus for that patient is no longer expedited recovery, but rather life-sustaining measures. Second, abortion of planned surgical procedure will qualify as a post-randomization exclusion. These patients do not undergo the intended surgical experience, will have different care pathways and goals, and are often discharged prior to 48 hours (length of time for the intervention). This exclusion will be defined as the patient being discharged home within 23 hours of anesthesia stop time, consistent with an 'observation' status rather than 'inpatient admission' to the hospital. Manual chart review will be performed to ensure appropriate exclusion. The occurrence of these exclusions will be tracked between study arms. Eligible patients will be consented for inclusion in the trial usually on the day of their surgery; patients returning for a follow up procedure that meets inclusion criteria will be reapproached for consent and rerandomized as appropriate.

Cohort Definition for Data Analysis

Intent-to-Treat Cohort

Intent-to-treat cohort includes all participants who are eligible and did not meet exclusion criteria specified in the study protocol.

Per-Protocol Cohort

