To better understand the potential efficacy of ketamine, a per protocol cohort will be analyzed which will include patients in both arms who did not have the study infusion stopped for adverse effects. The per-protocol cohort includes participants who finished the 48-hour post-operative infusion (either ketamine or placebo), as well as participants for whom the study infusion was intentionally discontinued early because the patient met appropriate recovery milestones and was preparing for discharge. However, this per-protocol cohort will exclude any patients in whom the study infusion was stopped for intolerance or side effects, including those patients who were discharged prior to 48 hours but had the post-operative study infusion stopped prior to 48 hours due to intolerances or side effects.

Treatment Arms

Randomization of treatment arms will occur in clusters of one week so that all patients in the same week will receive the same therapy (i.e., ketamine or placebo).

- A. **Intervention:** Patients will receive a weight-based (up to 100 kg max) intraoperative ketamine bolus (0.5 mg/kg) followed by continuous infusion (5 mcg/kg/min), and an additional postoperative ketamine infusion (2.5 mcg/kg/min, up to 100 kg max) for 48 hours.
- B. **Placebo:** Patients will receive an intraoperative saline bolus followed by continuous infusion of equivalent volume to study drug dosed for 5 mcg/kg/min, and an additional postoperative saline infusion for 48 hours at an equivalent volume of infusion as the intervention arm.

Outcomes

Primary Outcome

The primary outcome is the LOS in days for the placebo arm and the intervention (ketamine) arm. LOS is defined as the time between anesthesia start and the patient being discharged (patient physically leaving the hospital).

Secondary Outcomes

1. Total consumption of post-enrollment inpatient opioids in morphine milligram equivalents during the perioperative period to hospital discharge
2. The incidence of following surgical outcomes:
 - a. rapid response team calls
 - b. transfer to ICU (not including direct transfer from OR to ICU as these patients are excluded from the study) after patient has been sent to the PACU or floor
3. The incidence of the following indications or side effects requiring early cessation of the study medication, as documented by the provider at the time of discontinuing the order (from Best Practice Advisory, BPA)
 - a. Meeting milestones/preop for discharge

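### SAP secondary outcome 2b omits all direct OR-to-ICU transfers as excluded, but only intubated ones are, so an extubated direct ICU admission stays in the cohort and, read literally, goes uncounted

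*SAP*

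**What the plan says.** **The outcome.** Protocol 4.2 lists "surgical outcomes including rapid response, transfer to icu, and ileus" as a secondary outcome and puts no restriction on the route to the ICU. The SAP (Secondary Outcomes, item 2b) narrows the ICU component: "transfer to ICU (not including direct transfer from OR to ICU as these patients are excluded from the study". The item then counts only those transfers that follow arrival in the PACU or on the floor.

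**The exclusion.** Protocol 6.2 lists "direct transfer from operating room to ICU with endotracheal tube placed". The SAP (Study Population) repeats the condition for the first of its two post-randomization exclusions: "a patient directly transferred from the operating room to the Intensive Care Unit (ICU) with an endotracheal tube placed will not be included".

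**The analysis set.** The SAP says: "Intent-to-treat cohort includes all participants who are eligible and did not meet exclusion criteria specified in the study protocol". Its Main Analysis section makes this the cohort for the main analyses. Its paragraph on secondary analyses assigns each binary outcome a mixed-effect logistic regression, with no separate rule for patients admitted to the ICU directly from the OR.

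**The concern.** Item 2b justifies its omission by saying that the omitted patients are not in the study. Under both written exclusion rules this is true only of those who leave the OR intubated. For an extubated patient taken straight to the ICU, the omission has no stated basis.

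Such an admission also appears to fall between the plan's recording rules:

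- It is not an exclusion, so the SAP's tracking of exclusions by arm does not pick it up.
- It is not an outcome 2b event.
- It reaches outcome 3 only if the study drug is stopped early for one of the listed reasons.

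The admission comes after the study drug has been started in the OR, so its frequency could differ by arm. ICU transfer is one of three surgical outcomes named in protocol 4.2, under the aim on surgical outcomes in section 4. What is at stake is whether that comparison covers the ICU admissions of the patients actually analysed.

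**Working it through.** **Step 1. Set the rules side by side.** The plan states no figure for this outcome, so there is none to reproduce. The check is a comparison of text.

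| Patient's route from the OR | Excluded (protocol 6.2, SAP Study Population)? | In intent-to-treat cohort? | Event under 2b read literally? |
|---|---|---|---|
| Straight to ICU, intubated | Yes | No | Not applicable |
| Straight to ICU, extubated | No | Yes | No, unless a later transfer follows |
| PACU or floor, then ICU | No | Yes | Yes |
| PACU or floor, no ICU | No | Yes | No |

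The reason given in 2b fits the first row only. The second row is the gap. The last column of that row is inferred from the 2b definition, the cohort rule and the logistic model; no sentence in the SAP states it.

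**Step 2. See whether the rationale widens the exclusion.** One argument is specific to intubation: "A transfer to the ICU while intubated reflects the occurrence of a major, unintended, and unanticipated intraoperative event". Another would fit an extubated ICU patient equally well: "Enhanced Recovery After Surgery (ERAS) protocols are not followed in the ICU, and therefore there would be significant deviations from study protocol". Both are reasons offered for a criterion that keeps its endotracheal-tube condition. Neither changes who is excluded.

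**Step 3. Look for a bound in the documents.** The SAP (Power and Sample Size) and protocol section 12 expect about 30 post-randomization exclusions, and 1514 + 30 = 1544 agrees with the stated total. Those 30 cover intubated transfers and aborted procedures together. They do not bound extubated direct transfers, for which no rate is given.

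**Step 4. Illustrate with assumed rates.** Let d be the proportion going extubated straight to the ICU and t the proportion transferred later from PACU or floor. Treat the two groups as distinct, with N = 1514.

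- Admissions not counted = 1514 × d. For d = 0.5%, 1514 × 0.005 = 7.6, about 8. For d = 3%, 1514 × 0.03 = 45.4, about 45.
- Share of ICU admissions not counted = d / (d + t). The lowest value is at d = 0.5%, t = 5%: 0.005 / 0.055 = 9%. The highest is at d = 3%, t = 2%: 0.03 / 0.05 = 60%.

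The width of that range shows how little the documents settle.

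**Step 5. Illustrate the effect on the odds ratio.** Assume t = 3% in both arms, with d = 1% in one arm and 2% in the other.

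- Counted under 2b: 3% versus 3%, OR = 1.0.
- Any ICU admission: 4% versus 5%, OR = (0.05 / 0.95) / (0.04 / 0.96) = 0.05263 / 0.04167 = 1.26.

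**Step 6. Put that difference in proportion.** With 1514 / 2 = 757 per arm, 4% and 5% are 30.3 and 37.9 events. The standard error of the log odds ratio is √(1/30.28 + 1/37.85 + 1/726.72 + 1/719.15) = 0.249. The approximate 95% interval around 1.26 is exp(0.234 ± 1.96 × 0.249), or 0.77 to 2.06, before any allowance for clustering.

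**The case against.** **The phrase may be shorthand.** Item 2b may simply refer back to the exclusion defined earlier in the same SAP, with the tube condition left out by oversight. That is plausible. It is also possible that the authors meant to exclude every direct ICU transfer, since the argument about enhanced recovery in the ICU would support that. The two readings give different cohorts, neither is written in 2b, and neither says how an extubated direct admission is scored. The objection lowers certainty about the consequence but does not remove the mismatch.

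**Counting only transfers after PACU or floor is a legitimate definition.** It targets escalation of care after the first disposition, and a SAP may make a short protocol label operational. This stands. The fault is in the stated reason and the missing handling rule, not in the choice of endpoint.

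**Some of these events appear elsewhere.** Hemodynamic instability or another severe side effect that stops the study drug is recorded under outcome 3, and a prolonged stay enters the primary outcome. This is partly right, but neither route records an ICU admission as such.

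**The effect is small and could not be resolved.** The interval in the illustration runs from 0.77 to 2.06, so the trial could not distinguish 1.26 from 1.0. This stands for that example and is one reason for not pressing the point harder.

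**Stronger readings that the documents do not support.**

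- A reader might infer that the omission reverses the treatment effect. Rates can be chosen that do this: direct transfers at 1% versus 3% and later ones at 3% versus 2% give a counted OR of (0.02 / 0.98) / (0.03 / 0.97) = 0.66 against 1.26 for any ICU admission. Nothing in the documents makes those rates likely.
- A reader might infer that the omitted admissions follow the highest exposure in the trial. Only the infusion rate is highest in the OR (5 against 2.5 mcg/kg/min). The planned postoperative total is 2.5 × 60 × 48 = 7,200 mcg/kg, or 7.2 mg/kg. For an assumed 4-hour case, the intraoperative total is 0.5 + 4 × 0.3 = 1.7 mg/kg.

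**Conclusion.** The mismatch is certain on the text: 2b relies on an exclusion broader than the one written in protocol 6.2 and in the SAP. The consequence is a firm inference rather than a stated rule. If 2b is followed literally, an extubated patient admitted directly to the ICU is analysed as having had no ICU transfer, unless one occurs later.

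The size is unknown. The 9% to 60% uncounted share and the shift from 1.0 to about 1.26 rest wholly on assumed rates and should not be cited as estimates. The true number could be very small.

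The reach is one binary secondary outcome; the primary outcome and the sample size are untouched. The SAP should still be corrected, because its rule rests on a premise that the documents contradict and the correction is cheap.

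**What to change.** 1. In SAP item 2b, restate the reason so that it says only direct transfers with an endotracheal tube in place are excluded from the study, in agreement with protocol 6.2 and the SAP Study Population section.
2. Keep transfer after PACU or floor as the stated outcome, and say explicitly that an extubated direct admission is not an event under it.
3. Report extubated direct OR-to-ICU admissions by arm as a separate row.
4. Add a sensitivity mixed-effect logistic model, with the same covariates, for any ICU admission in the analysis cohort (extubated direct plus PACU or floor).

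The cost is a wording change, one table row and one model. The route from OR to ICU must be identifiable in the record. The protocol describes abstraction of encounter data from the EMR but does not list this item, so its availability should be confirmed. Some direct admissions may be planned monitoring stays, and the documents list no field that separates these from unplanned ones. For that reason the combined outcome belongs in a sensitivity analysis and should not replace 2b.

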 - b. Mild side effects, but prefers discontinuation
 - c. Debilitating hallucinations
 - d. Debilitating dizziness
 - e. Hemodynamic instability
 - f. Other severe side effect

4. The incidence of ileus requiring gastric decompression as defined by orogastric or nasogastric tube placement in the postoperative period

Exploratory Outcomes

1. Instances of reoperation within the index encounter
2. VUMC hospital readmissions within 30 days post-discharge (not including ED visits)

Design Considerations

Randomization

Randomization will occur in clusters of one week. All patients in the same week will receive the same therapy (ketamine or placebo), with the selection being determined by a pre-generated random sequence.

Power and Sample Size

We anticipate the use of ketamine will reduce LOS following surgery start. To determine how long this trial will need to run to have sufficient power to detect a meaningful difference, we assumed 85% power, a type I error rate of 5%, and a 10% reduction in LOS. We estimated the within period correlation from preliminary data concerning the length of stay for major abdominal surgeries to be about 0.014. Given these assumptions, about 1514 patients would need to be included overall. An increase in sample size is necessary to accommodate for the two post-randomization exclusions that are pre-specified. We expect approximately 30 participants to be impacted by these post-randomization exclusions and will therefore increase the sample size by 30 to account for this exclusion (n=1544). Given surgical volumes, we expect 20 patients to be enrolled each week, and for the trial to last approximately 18 months.

Statistical Approach

Descriptive Analysis

We will describe the study cohort both overall and by treatment arm. To characterize the study sample, demographic and clinical data will be described. Categorical variables will be described using frequencies and proportions; continuous variables will be described using means and standard deviations as well as medians and interquartile ranges (IQR). Missingness will be recorded for each variable. To further assess the distribution of variables, graphical summaries will be displayed using graphs such as boxplots, dotplots, and/or histograms. No statistical testing will be performed to compare characteristics between groups. At a minimum, the following baseline variables will be described:

- Age (years)
- Sex assigned at birth (male, female, unknown)
- Race
 - Caucasian

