Secondary analyses: The secondary outcomes will be analyzed with the same covariates. A mixed-effect proportional odds model will be used to evaluate difference in opioid use in the hospital between the intervention and placebo arms. For each of the binary outcomes, a mixed-effect logistic regression will be used to compare the odds of events between the two arms.

Exploratory analyses: The exploratory outcomes will be presented in tables comparing the incidences of reoperation and hospital readmission within 30 days post-discharge between two arms.

Differential Treatment Effects

Differential treatment effects will be explored by examining the interaction between the treatment indicator and each variable that potentially interacts with treatment, one variable at a time, but subgroup analysis will not be performed. The variables we consider include sex, opioid naïve status, type of surgical procedure (colorectal, ventral hernia, or surgical oncology), epidural vs. truncal nerve block, known history of depression, and known history of PTSD.

References

5. Mercadante S. Opioid Analgesics Adverse Effects: The Other Side Of The Coin. *Curr Pharm Des.* 2019;25:1-6. doi:10.2174/1381612825666190717152226.

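### No planned analysis estimates how often the study infusion is stopped for intolerance: SAP secondary outcome 3 splits these stops into five side-effect reasons and never combines them

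*SAP*

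**What the plan says.** Protocol 4.2(c) sets as a secondary outcome "the incidence of side effects, including hallucinations, sedation, adverse reactions requiring early cessation". Stops for recovery are not mentioned there.

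The SAP (Outcomes, Secondary Outcomes, item 3) restates this as "The incidence of the following indications or side effects requiring early cessation of the study medication, as documented by the provider", recorded when the order is discontinued. Six lettered reasons follow:

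- (a) "Meeting milestones/preop for discharge"
- (b) "Mild side effects, but prefers discontinuation"
- (c) "Debilitating hallucinations"
- (d) "Debilitating dizziness"
- (e) "Hemodynamic instability"
- (f) any other severe side effect

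On analysis, the SAP (Main Analysis, Secondary analyses) applies the primary model's covariates to the secondary outcomes and adds: "For each of the binary outcomes, a mixed-effect logistic regression will be used to compare the odds of events between the two arms". It does not say whether item 3 is one binary outcome or six.

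The SAP's per-protocol cohort does separate the two kinds of stop. It keeps patients whose infusion ended early because they had recovered, and it removes, as a single class, those whose infusion was stopped for intolerance or side effects. Under Main Analysis that cohort is used only for length of stay and opioid consumption.

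**The concern.** Tolerability is what has to be weighed against any gain in length of stay or opioid use. The basic comparison is the proportion in each arm whose infusion had to be stopped because of the drug's effects. Read in the natural way, as separate outcomes, the plan models each reason by itself and never models that proportion.

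This has two consequences. First, the harms are divided among five reasons that are each likely to be uncommon, so a real excess of intolerance could appear as several inconclusive odds ratios. Second, each sparse reason is to carry the full covariate set, which few events cannot support. If the analysts respond by combining reasons later, they will choose the grouping after stop reasons by arm can be seen, and preventing that is a purpose of an SAP.

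**Working it through.** There is no planned figure to reproduce: neither document gives a rate, sample size or power for early cessation. The check therefore has a textual part and an illustration under assumed rates.

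**Text.**

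1. Protocol 4.2(c) concerns side effects, including adverse reactions that force cessation.
2. SAP item 3 has one non-harm reason (a) and five side-effect reasons (b) to (f).
3. The SAP's Secondary analyses paragraph supplies one model per binary outcome and names no combination of reasons.
4. The per-protocol definition uses the class of intolerance or side-effect stops, but only to select patients for two other outcomes.

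So the class exists in the plan, and no between-arm estimate of it is planned.

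**Inputs from the documents.**

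- Total 1514 before the allowance of 30 (SAP, Power and Sample Size). Assuming 1:1 allocation, 1514 / 2 = 757 per arm.
- Within-period correlation 0.014, estimated for length of stay and borrowed here for binary outcomes.
- 20 patients per week as planned. Protocol section 12 also reports about 15.
- Type I error 5%, taken as two-sided.

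**Assumed.** Each of five mutually exclusive reasons occurs in 1% of placebo and 2% of ketamine patients. Any of (b) to (f) is then 5 × 1% = 5% versus 5 × 2% = 10%.

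**Design effect.** 1 + (20 − 1) × 0.014 = 1.266, so the effective n per arm is 757 / 1.266 = 597.9. At 15 per week: 1 + 14 × 0.014 = 1.196, giving 632.9.

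**Power (unadjusted, normal approximation).** Power = Φ[(d − 1.96 × se0) / se1], with se0 = √(2p̄(1 − p̄)/n) and se1 = √([p1(1 − p1) + p2(1 − p2)]/n).

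- One reason, n = 757: se0 = √(0.02955/757) = 0.00625 and se1 = √(0.0295/757) = 0.00624. Then (0.01 − 0.01225)/0.00624 = −0.36, power 36%.
- One reason, n = 597.9: se0 = 0.00703 and se1 = 0.00702. Then (0.01 − 0.01378)/0.00702 = −0.54, power 30%.
- Any of (b) to (f), n = 757: se0 = √(0.13875/757) = 0.01354 and se1 = √(0.1375/757) = 0.01348. Then (0.05 − 0.02653)/0.01348 = 1.74, power 96%.
- Any of (b) to (f), n = 597.9: se0 = 0.01523 and se1 = 0.01516. Then (0.05 − 0.02986)/0.01516 = 1.33, power 91%.

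**Range over assumed rates** (same formula, n = 597.9):

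| One reason | Power | Any of (b)-(f) | Power |
|---|---|---|---|
| 0.5% vs 1% | 17% | 2.5% vs 5% | 62% |
| 1% vs 2% | 30% | 5% vs 10% | 91% |
| 2% vs 4% | 53% | 10% vs 20% | 99.8% |

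At 15 per week the middle row becomes 31% and 92%.

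**Events against model size.**

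- One reason: 757 × (0.01 + 0.02) = 22.7, about 23 events.
- Any of (b) to (f): 757 × (0.05 + 0.10) = 113.6, about 114 events.
- The SAP names eleven covariates. Four are treated here as continuous: age, BMI, Elixhauser score and intraoperative time. At an assumed two terms per spline and one term for each of the other seven, the fixed effects are 4 × 2 + 7 + 1 for treatment = 16 coefficients, besides the intercept and the random effect.
- Events per coefficient: 22.7 / 16 = 1.4 for one reason, against 113.6 / 16 = 7.1 for the combined outcome.

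**The case against.** **A stronger reading that the text does not support.** A reader might infer that item 3 counts a benefit together with harms, because (a) stands in the same list as (b) to (f). No passage sums the six reasons. The heading speaks of indications or side effects, the reasons are lettered separately, item 2 uses the same layout for two plainly distinct events, and the analysis sentence refers to each binary outcome. Separate outcomes is the natural reading.

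A reader might also infer that a merged outcome would make a ketamine arm with faster recovery and worse tolerance look neutral. The direction is wrong: both would raise the count of early stops. For example, milestone stops of 20% placebo versus 25% ketamine plus side-effect stops of 5% versus 10% give 25% versus 35%.

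**The case for leaving the plan alone.**

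- Protocol 4.2(c) is a list of side effects and does not demand a composite, so reporting by reason is compatible with it. This stands, but the list does name adverse reactions that force cessation.
- Protocol section 12 puts effect sizes ahead of p-values and reports events as rates with confidence intervals. This softens the power argument. However, an imprecise odds ratio for a sparse reason is a weakness of estimation too.
- If only one reason is recorded per patient, the arm-level rates for (b) to (f) add up to overall intolerance. That is so, but the documents do not state that reasons are exclusive, and a sum made by the reader has no adjusted estimate or cluster-aware interval.
- A composite joins mild side effects with severe ones and can hide a shift in severity. This is fair, and it is why the components must be tabulated.
- Every stop rate in the working is assumed. This also stands.

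**Conclusion.** The concern holds in this form: as written, the plan models sparse individual stop reasons with a heavy covariate set and omits the overall rate of stopping for intolerance. The gap can be read directly from the documents and needs no assumption about rates. Its numerical size does: it rests on equal, mutually exclusive reasons, 1:1 allocation, a two-sided 5% test, unadjusted power and a correlation borrowed from length of stay. Across the rates tried, with clustering at 20 per week, one reason has 17-53% power and the combined outcome 62-99.8%. The combined outcome is the more precise in every case tried. It would gain less if only one reason differed between arms.

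This is a change that should be made to one secondary outcome.

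**What to change.** In SAP secondary outcome 3:

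1. Define one binary outcome: study infusion stopped early for intolerance or side effect, meaning any of (b) to (f). Fit the planned mixed-effect logistic model to it.
2. Tabulate (b) to (f) by arm as rates with confidence intervals, so that mild and severe reasons stay distinguishable.
3. Report (a) separately as a recovery measure.

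The cost is SAP wording. The stop reasons are already to be recorded, and the per-protocol cohort already needs the same grouping, so no new data and no change to care are involved. The small downside is that individual reasons are described rather than modelled.

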## **9. Risks:**

Ketamine is an analgesic that has been proven to reduce opioid consumption after surgery. It also has a role in reducing the development of chronic pain. Compared to opioids, ketamine has a favorable side-effect profile, including the maintenance of respiratory and cardiovascular stability. Ketamine does not act at the mu opioid receptor, and therefore is not associated with nausea, itching, constipation, and tolerance.

We have been safely utilizing perioperative ketamine VUMC for several years as part of our enhanced recovery pathways.

Ketamine is a controlled substance and is highly regulated, recorded, and tracked. Patients are evaluated daily at the bedside by our Preoperative Medicine Service, and patients are screened for side effects of ketamine on daily rounds. Nurses are trained to immediately report any suspicion of an adverse ketamine reaction to a member of our team, who is in-house 24/7.

**Adverse reactions to ketamine:** Adverse reactions and allergies to ketamine are routinely reviewed by both medical providers and pharmacy personnel prior to ordering and administering the drug. Ketamine is a controlled substance and is highly regulated, recorded, and tracked. Patients are evaluated daily at the bedside by our Preoperative Medicine Service, and patients are screened for side effects of ketamine on daily rounds. Nurses are trained to immediately report any suspicion of an adverse ketamine reaction to a member of our team, who is in-house 24/7.

**Selection of patients:** Only patients receiving care through our enhanced recovery pathway (which includes the standard administration of ketamine) will be eligible for participation.

**Ineffective pain control:** Patients with breakthrough pain will receive routine treatment guided by our preoperative protocols and discretion of medical providers.

**Breach of confidentiality:** The investigators have access to the medical data as part of their job standing. All database work will be performed on VUMC approved and password protected servers that are physically located in the VUMC computing environment and maintained by VUMC security standards. Only the PI and KSP will have access to study specific data.

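### SAP secondary outcome 3 counts reasons for stopping the infusion and names no sedation category, so the side-effect incidence listed in Protocol 4.2(c) is only partly estimated

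*SAP*

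**What the plan says.** Protocol 4.2, item c, lists as a secondary outcome "the incidence of side effects, including hallucinations, sedation, adverse reactions requiring early cessation". Protocol section 12 adds that event occurrence will be reported as rates with confidence intervals and compared by logistic regression.

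The SAP (Outcomes, Secondary Outcomes, item 3) replaces this with "The incidence of the following indications or side effects requiring early cessation of the study medication". The source is the provider's entry in the Best Practice Advisory when the order is discontinued. There are six categories:

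- Category a, "Meeting milestones/preop for discharge", is a recovery reason and not a side effect.
- Categories b, "Mild side effects, but prefers discontinuation", and f, "Other severe side effect", do not name the type of effect.
- The other three do name it: c is "Debilitating hallucinations", d is dizziness of the same grade, and e is unstable hemodynamics.

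Under Main Analysis, the SAP assigns each binary secondary outcome a mixed-effect logistic regression.

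Two other protocol passages bear on the point. Section 9 says that "patients are screened for side effects of ketamine on daily rounds". The consent language in section 7 tells patients that record data will be used to evaluate whether they have any side effects.

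**The concern.** The two documents define the same secondary outcome differently. In the protocol, the natural unit is a patient who had a side effect. In the SAP, it is a patient whose infusion was stopped and for whom a reason was recorded. A patient who hallucinates or becomes sedated but completes the infusion contributes no event under the SAP.

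What is at stake is the safety statement in the final report. Ketamine is being tested as one component of a multimodal bundle, so a length-of-stay result will be weighed against tolerability. If the only tolerability measure is discontinuation, similar stop rates in the two arms could be read as no excess of side effects, which that measure cannot show. Sedation is one of only two effects the protocol names, and it would have no figure of its own.

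**Working it through.** No planned figure is available to reproduce: neither document gives a side-effect rate, or a power or sample-size statement for this outcome. The check sets the definitions side by side. The protocol line can be read in two ways. In the broad reading, the early-cessation qualifier attaches only to adverse reactions. In the narrow reading, it attaches to the whole list.

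| Event | Protocol, broad | Protocol, narrow | SAP item 3 |
|---|---|---|---|
| Debilitating hallucinations, infusion stopped | counted | counted | counted, category c |
| Milder hallucinations, infusion stopped | counted | counted | category b, type not identified |
| Hallucinations, infusion continued | counted | not counted | not counted |
| Sedation, infusion stopped | counted | counted | b or f, not identifiable |
| Sedation, infusion continued | counted | not counted | not counted |
| Other adverse reaction, infusion stopped | counted | counted | counted, b or d to f |

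1. **Broad reading.** Of the three components named in the protocol, adverse reactions requiring cessation are covered, hallucinations are covered only when debilitating and followed by stopping, and sedation has no estimate.

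2. **Narrow reading.** The rows for a continued infusion drop out. What remains is mainly sedation, which the protocol names and the SAP does not. A small remainder is milder hallucinations that stopped the infusion, which category b holds without their type.

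3. **Other outcomes.** The remaining SAP secondary outcomes are opioid consumption, rapid response calls, ICU transfer and ileus requiring decompression. The exploratory outcomes are reoperation and readmission. None measures sedation or hallucinations.

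4. **Which text is current.** SAP version 1.0 is dated September 6, 2023. Protocol section 8 reports in the past tense that enrollment resumed on September 18, 2023. The protocol text therefore appears to be the later of the two and still carries the wider outcome. The SAP gives no reason for the narrower one.

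5. **Effect on the comparison.** Let p be the true incidence in an arm and f the share of events that lead to stopping. The SAP counts f × p. If f is the same in both arms, the ratio is preserved: (f × p1) / (f × p0) = p1 / p0. The absolute difference shrinks to f × (p1 − p0), and fewer events are available to detect it. The documents give no value for p or f, so the size of the shortfall cannot be calculated.

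**The case against.** The best defence is that item 3 is openly labelled as early cessation. The SAP does not present stop rates as general side-effect incidence, and a reader who inferred that it does would be going beyond its words. It may simply be making a terse protocol line operational, much as it turns ileus into ileus requiring gastric decompression. The milestone category is not an error either: the item covers indications as well as side effects, milestones have their own line, and the SAP's per-protocol cohort definition already separates milestone stops from stops for intolerance.

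The defence can add that serious harm has other routes to detection through rapid response calls and ICU transfers. Both arms are blinded, so a similar stopping share in each is plausible, and the relative comparison for uncommon events would then be largely preserved.

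All of this stands, and it limits the point. It does not remove it. On either reading of the protocol line, sedation is a named item without a SAP category. Rapid response calls and ICU transfers do not measure sedation or hallucinations as such. A preserved ratio, if the stopping shares are in fact equal, still leaves absolute incidence unestimated and the comparison less precise.

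**Conclusion.** The concern holds as a mismatch between protocol and SAP. The SAP narrows side-effect incidence to provider-recorded reasons for stopping and names no sedation category. The incidence of sedation, and of hallucinations that were not debilitating or did not stop the infusion, cannot be estimated from it. On the narrow reading of Protocol 4.2(c), the gap reduces mainly to sedation.

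Two stronger readings are tempting but unsupported. A reader might infer that the trial cannot answer its safety question. That goes too far, because adverse reactions leading to cessation are covered and compared between arms. A reader might also infer that sedation would be reported as zero. It would not: the SAP would give no sedation figure at all, and cases that led to stopping may lie unidentified in categories b or f.

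No numerical understatement is claimed, since any such figure would rest on a stopping share that the documents do not supply. The outcome is secondary, so the length-of-stay analysis is unaffected. The conclusion assumes that the SAP is followed as written and that no further side-effect definition exists outside these documents.

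**What to change.** Reconcile Protocol 4.2(c) and SAP item 3 before the analysis, by one of two routes for each effect.

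- **Retrievable from the EMR.** Protocol section 8 lists nursing records and clinical notes among the data types, and section 9 describes daily side-effect screening. Neither section says that hallucinations or sedation are held in structured fields, so check this first. If they are, add the incidence of each by arm for all patients, whether or not the infusion was stopped. State the field and the time window, and use the mixed-effect logistic model already planned.
- **Not retrievable.** Amend Protocol 4.2(c) and label SAP item 3 as discontinuation of study infusion by reason. Limit the safety conclusion to side-effect-related discontinuation, and say that a null result does not show the absence of excess side effects.

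On either route, keep milestone stops out of any side-effect total. Do not count on separating sedation out of categories b and f: the documents do not say that free text accompanies the recorded reason.

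The cost is a modest extra data extract on the first route and a narrower safety claim on the second. Neither changes the sample size or the primary analysis.
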